Clinical Evaluation of the Levita Robotic Platform

Protocol Number: CP007
Revision: A
January 12, 2021

Sponsor: Levita Magnetics
[name]
Title: CEO and Founder
Email: [contact]
[contact]

Sponsor Signature: _____

Sponsor Name: [name]

CONFIDENTIALITY STATEMENT

This study is confidential in nature. All information related to this study is considered proprietary and should not be made available to those not directly involved in this study. Authorized recipients of this information include Investigators and co-Investigators, other health care personnel necessary to conduct the study, and Clinical Investigation Ethics Committees and Institutional Review Boards. The personnel provided with data from this study are hereby informed of its confidential and proprietary nature. Release of these data to individuals other than those listed above requires the prior written permission of Levita Magnetics.

PROTOCOL REVIEW PAGE

STUDY TITLE: Clinical evaluation of the Levita Robotic Platform
PROTOCOL: CP007
REVISION: A

Investigator's Statement: I agree to conduct this clinical study in accordance with the design and specific provisions of this protocol; modifications to the study or protocol are acceptable only with a protocol amendment approved by the Study Sponsor and Ethics Committee (EC) if required. I agree to await EC approval for the protocol and informed consent before initiating the study, to obtain informed consent from subjects prior to their enrollment in the study, to collect and record data as required by this protocol and case report forms, submit all reports as required by this protocol, provide the requested financial information, and to maintain study documentation for the period of time detailed in this protocol.

Investigator Signature	Date of Signature
Investigator Name:	

Protocol Synopsis

Title:	Clinical Evaluation of the Levita Robotic Platform
Study Objective:	The purpose of this study is to evaluate the safety and feasibility of the Levita Robotic Platform (LRP) used with the Levita Magnetic Surgical System (MSS).
Study Design:	Prospective, multi-center, single-arm, open label study designed to assess the safety and feasibility of the use of the Levita Robotic Platform with the Levita Magnetic Surgical System in laparoscopic procedures.
Enrollment Size and Number of Sites:	Up to 100 subjects in up to 5 clinical sites in Chile
Subject Population:	All patients at least 18 years of age presenting for elective laparoscopic surgery are potential candidates.
Safety Outcomes:	All adverse events will be captured and reported. Adverse events will be summarized by relatedness to the device and/or procedure, seriousness and level of severity. If device related, AEs will be further characterized as to relationship to the MSS the LRP or both.
Feasibility Outcomes:	
Ability to utilize the Levita MSS with the LRP as intended in laparoscopic procedures. The following outcomes will be considered in this feasibility study:
 
 1. The LRP is able to engage, move, and decouple with the MSS as intended / controlled by the surgeon 2. The LRP is able to provide adequate endoscopic visualization via a conventional endoscopic system as intended / controlled by the surgeon 3. The procedure is successfully performed with the MSS and LRP. 4. The MSS or the LRP cannot be successfully used and due to a MSS or LRP performance issue the procedure must be converted to an open procedure.
Inclusion Criteria:	
Subjects must meet ALL of the following inclusion criteria to be eligible for participation in the study:
 
 • Subject is at least 18 years of age • Subject is scheduled to undergo elective laparoscopic procedure • Subject signs a written Informed Consent Form (ICF) to participate in the study prior to any study required procedures

Exclusion Criteria:	
Subjects must be EXCLUDED from participation in this study if ANY of the following exclusion criteria are met:
 
 • Subjects with pacemakers, defibrillators, or other electromedical implants • Subjects with ferromagnetic implants • Subjects with significant comorbidities: cardiovascular, neuromuscular, chronic obstructive pulmonary disease, and urological disease (renal failure) • Subjects with a clinical history of impaired coagulation confirmed by abnormal blood tests • Subject has an anatomical abnormality or disease of intended target tissue noted after initiation of index procedure that would prevent device use • Subject is pregnant or wishes to become pregnant during the length of study participation • Subject is not likely to comply with the follow-up evaluation schedule • Subject is participating in a clinical trial of another investigational drug or device

APPENDIX 1: INFORMED CONSENT FORM

1 INTRODUCTION

1.1 Background and Rationale

Since the introduction of minimally invasive surgery (MIS) in the 1980's, laparoscopy has become the preferred approach for intra-abdominal procedures. With limited access to the surgical field, one of the key requirements of laparoscopic surgery is the ability to achieve and maintain adequate visualization of the surgical target throughout the procedure. During certain MIS procedures, the patient's internal organs can block or obscure the surgical view. A number of surgical instruments (graspers or retractors) have been developed to help mobilize abdominal organs to obtain an adequate surgical view during MIS procedures. Most of these instruments require an additional abdominal wall puncture/incision, leading to potentially increased complications. These complications include risk of postoperative pain, additional scars, injury to major blood vessels and bowel, infection, incision-related hernias, and chronic incisional pain, among others.

To maximize the benefits of MIS, robotic surgery was developed more than 30 years ago. However, the use of the robotic technology has not resulted in demonstrated clinical benefit and the same number of incisions are typically required in robotic procedures (Tan et al; Leal and Campos). Nevertheless, one of the advantages of a robotic platform is that the surgeon has full control of all instruments during the surgery.

One of the goals of MIS is a reduction in the number of abdominal incisions, resulting in less postoperative pain, reducing the risk of incision-related complications, improving the cosmetic results, and increasing overall patient satisfaction after surgery (Nguyen et al). Levita Magnetics developed the Levita® Magnetic Surgical System (MSS) for tissue/organ mobilization. The MSS allows the surgeon to move tissue/organs out of the visual field without requiring a dedicated incision/port for the tool.

Laparoscopic procedures often require several clinical team members to manage the instruments and camera. Ideally only one clinician, who would provide direct control of all the internal surgical tools, would be required. This would both improve the operating environment and reduce the cost of the procedure by decreasing the number of required personnel.

Recently, Levita has developed a Robotic Platform (LRP) to assist in external management of the controlling magnet which would reduce required personnel and give control of all surgical tools to the same surgeon. The LRP replaces the commercially available surgical support arm that is currently used with the MSS.

The safety and effectiveness of the MSS has been demonstrated for the retraction of the gallbladder during cholecystectomy (Rivas et al.). This pivotal

study, published in the Annals of Surgery and conducted in Chile, supported the marketing clearance of the MSS in the United States in 2016. Initial US experience (Haskins et al.), performed at the Cleveland Clinic, confirmed the results described in the Rivas publication. The MSS has also been used successfully for liver mobilization in bariatric procedures at Duke Regional Medical Center in a series of 40 patients (Davis et al.) As use of the MSS for laparoscopic procedures expands additional data collection is ongoing to detail clinician's experiences with this system in various other laparoscopic procedures.

This current study is intended to evaluate the safety and feasibility of the Levita Robotic Platform when used with the Magnetic Surgical System for laparoscopic procedures.

2 SURGICAL SYSTEM DEVICE DESCRIPTION

The MSS is composed of three components: the Detachable Grasper, the Delivery/Retrieval Shaft (together, the “Magnetic Grasper Device”), and an external Magnetic Controller mounted on a Robotic Platform.

The Detachable Grasper and Delivery/Retrieval Shaft make up the Magnetic Grasper Device (**Figure 1**). Once the Magnetic Grasper Device is inserted through an access port and the Grasper is attached to the desired tissue, the Detachable Grasper can be detached from the Delivery/Retrieval Shaft and controlled externally using the Magnetic Controller. Traction of the tissue is maintained through the magnetic field attraction between the Detachable Grasper and the Magnetic Controller. The Magnetic Grasper Device is operated by hand and is inserted into the abdominal cavity through a ≥ 10 mm laparoscopic trocar port. The Magnetic Grasper Device is single-use, disposable, and provided sterile to the user.

[figure not shown]

Figure 1. Magnetic Grasper Device

The Magnetic Controller mounted on the robotic arm (**Figure 2**) emits a magnetic field that attracts the Detachable Grasper. Once the Detachable Grasper is attached to the desired tissue/organ and detached from the Delivery/Retrieval Shaft, the robot arm brings the Magnetic Controller to the external surface of the abdominal wall so that it can magnetically couple to the internal Detachable Grasper. Under control of the surgeon, the LRP moves the Magnetic Controller along the surface of the abdomen. When the Magnetic Controller moves, the Detachable Grasper follows, thus retracting the internal tissue/organ to a location of the surgeon's choice. The external Magnetic Controller and the LRP is reusable, provided non-sterile to the user, and must be placed in an off-the-shelf sterile bag prior to use.

[figure not shown]

Figure 2. Magnetic Controller

The Levita Robotic Platform (**Figure 3**) includes two robotic arms, control unit(s), and control software. A handheld and/or foot-operated control pad allow for LRP control by the surgeon or surgical assistant. One arm of the LRP attaches the Magnetic Controller using the arm mount of the Magnetic Controller and the second robotic arm attaches a conventional laparoscopic camera.

[figure not shown]

Figure 3. Levita Robotic Platform. One arm is mobilizing the External Magnetic Controller (external magnet) and the second arm is mobilizing a conventional laparoscopic camera.

The LRP is certified to international electrical safety and software standards for use in medical products. The design of the LRP includes several redundant safety features which make it well suited for use with the MSS in the operating room environment. These features include hardware and software safety controls including requirement for an enabling switch, an emergency stop, and controls for the workspace, velocity and axis torque of the robot. As noted, the LRP is provided non-sterile to the user, and must be placed in an off-the-shelf sterile bag prior to use.

3 INDICATION FOR USE

The Magnetic Surgical System is designed to grasp, hold, retract, mobilize, or manipulate soft tissue and organs in minimally invasive procedures. The Robotic Platform is an accessory designed to facilitate use of the Magnetic Surgical System in a hands-free manner.

4 STUDY PURPOSE AND OBJECTIVE

The purpose of this study is to evaluate the safety and feasibility of the Robotic Platform used with the Levita Magnetic Surgical System in laparoscopic procedures.

5 STUDY ENDPOINTS

The following endpoints will be evaluated in all subjects who undergo laparoscopic procedures using the Robotic Platform and Magnetic Surgical System.

5.1 Safety Outcomes

All adverse events will be captured and reported. Adverse events will be summarized by relatedness to the device and/or procedure, seriousness and level of severity. If device related, AEs will be further characterized as to relationship to the MSS the LRP or both.

5.2 Feasibility Outcomes

Ability to utilize the Levita MSS with the LRP as intended in laparoscopic procedures. The following outcomes will be considered in this feasibility study:

1. The LRP is able to engage, move, and decouple with the MSS as intended / controlled by the surgeon
2. The LRP is able to provide adequate endoscopic visualization via a conventional endoscopic system as intended / controlled by the surgeon
3. The procedure is successfully performed with the MSS and LRP.
4. The MSS or the LRP cannot be successfully used and due to a MSS or LRP performance issue the procedure must be converted to an open procedure.

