9.2 Sample Size Justification

This is a single-arm, multi-center, investigational study to understand the safety and feasibility of the use of the LRP with the MSS. A sample size of 100 subjects was planned to allow use of the system in a number surgeons and a number of different types of laparoscopic procedures. It is expected that enrollment of 100 subjects will provide appropriate information regarding the safety and feasibility of the LRP and MSS in laparoscopic procedures.

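### Feasibility outcomes 3 and 4 pool the MSS and LRP with no device attribution, and the 5.3 conversion rate counts MSS causes only, so failures and conversions cannot be assigned to the LRP as defined

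*Combined protocol and SAP*

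**What the plan says.** Section 5.2 lists four feasibility outcomes. Outcomes 1 and 2 are framed on the robot: "The LRP is able to engage, move, and decouple with the MSS as intended / controlled by the surgeon" and "The LRP is able to provide adequate endoscopic visualization via a conventional endoscopic system as intended / controlled by the surgeon". Outcome 3 is joint success: "The procedure is successfully performed with the MSS and LRP". Outcome 4 is failure of either device, where "due to a MSS or LRP performance issue the procedure must be converted to an open procedure". No rule assigns a failure of any of these to one device.

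Adverse events are treated differently. Section 5.1 says "If device related, AEs will be further characterized as to relationship to the MSS the LRP or both", and 12.4.1 has the investigator judge by cause whether an event relates to the MSS, the LRP or both.

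On the device boundary, section 2 names as the third MSS component "an external Magnetic Controller mounted on a Robotic Platform". It describes the LRP as the arms, control units and software, one arm of which carries and moves that controller.

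Section 5.3 lists malfunctions of both devices, but defines the conversion rate by poor performance of the MSS alone. Section 7.4 collects conversion to open surgery without listing a cause, and lists neither the operation performed nor the organ retracted.

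On prior experience, section 1.1 states "The safety and effectiveness of the MSS has been demonstrated for the retraction of the gallbladder during cholecystectomy" and adds a 40-patient liver series in bariatric surgery. Eligibility in 7.1.1 is any elective laparoscopic procedure, and 9.2 justifies the sample size partly by "a number of different types of laparoscopic procedures".

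**The concern.** The LRP is what is new here: section 1.1 says it takes the place of the support arm now used with the MSS. A feasibility study should tell the sponsor what to correct. A pooled count of failures does not, because a robot that fails to hold position and a grasper that does not suit a given tissue add to the same total but call for different next steps. The plan already accepts, for adverse events, that the two devices need separating.

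Two features make separation harder afterwards. The magnet belongs to the MSS on paper but is moved by the robot, so sites could code the same coupling failure differently. And the trial may mix organs with cited MSS results and organs without them, while 9.1 plans no tabulation by procedure or organ.

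**Working it through.** **1. Figure to reproduce.** There is none. Sections 9.1 and 9.2 give no expected rate, performance goal, alpha, power or precision target, only a planned maximum of 100 subjects. The point concerns definitions, so the main check is to set the sections side by side.

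**2. Attribution by outcome.**

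| Item | Device named | Split by device stated? |
|---|---|---|
| 5.1 adverse events | MSS, LRP | Yes: MSS, LRP or both |
| 5.2 outcome 1 | LRP acting on MSS | No; unclear at the Magnetic Controller |
| 5.2 outcome 2 | LRP with a conventional endoscope | No MSS part involved; an endoscope fault is not separated |
| 5.2 outcome 3 | MSS and LRP jointly | No |
| 5.2 outcome 4 | MSS or LRP | No |
| 5.3 malfunctions | MSS and LRP | Both named; no assignment rule |

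**3. Conversion appears in three forms.** Section 7.4 collects any conversion to open surgery, 5.2 outcome 4 counts those due to either device, and 5.3 counts those due to the MSS. A conversion caused by the LRP alone is in the first two and not the third.

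**4. Size of the ambiguity.** The documents give no failure rate, so the counts below are assumptions, with n = 100 from 9.2. If x subjects meet outcome 4 and no device is recorded, the LRP-attributable count can lie anywhere from 0 to x. Exact (Clopper-Pearson) 95% intervals at the two ends:

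- For 0/100, the upper limit is 1 − 0.025^(1/100) = 3.6%, so the interval is 0 to 3.6%.
- For x = 2, the range runs from 0/100 (0 to 3.6%) to 2/100 (0.2% to 7.0%).
- For x = 5, the range runs from 0/100 (0 to 3.6%) to 5/100 (1.6% to 11.3%).
- For x = 0, there is nothing to split, and 3.6% bounds either device.

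The 5.3 rate moves with the same unknown. If k of 5 device-related conversions were due to the LRP alone, outcome 4 is 5/100 = 5% whatever k is, while the 5.3 rate is (5 − k)/100, anywhere from 5% (k = 0) to 0% (k = 5).

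**5. Are failures needing attribution likely?** The chance of at least one in 100 is 1 − (1 − p)^100. For assumed true rates p of 1%, 2% and 5% it is 63%, 87% and 99%. Some cases are likely even at low rates.

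**6. Case mix.** The MSS results cited in 1.1 concern gallbladder and liver. Nothing in 7.1.1 limits the trial to those, and without the operation and organ as listed data items in 7.4 the split by earlier experience is not assured.

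**The case against.** The strongest reply is that the trial answers the question it asks. The objective in section 4 is the robot used with the MSS, and section 3 calls the platform an accessory. Joint success is a natural outcome for that objective. This stands, and it limits the point: the gap is in attribution, and the combination can still be assessed.

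A reader might go further and infer that the trial cannot say whether the LRP itself is feasible. The documents do not support that. Outcomes 1 and 2 are framed on the robot, and outcome 2 involves no MSS part.

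A reader might also infer that no cause of failure is recorded. That cannot be shown. The CRFs are not among the documents; outcome 4 itself requires a judgement that a device was responsible; and malfunctions (5.3), device observations and procedure video (7.4) and device deficiencies (12.6) are all collected. With at most 100 subjects, a few failures could be reviewed one by one. What remains is that no rule is stated for sorting this material, so attribution would be made after the event.

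Nor does the text send an injury from robot pressure to the MSS. Section 12.4.1 attributes by cause, whatever list a component is on, and 5.1 offers both as an answer.

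Finally, it would be too strong to say that the MSS will be used on untried organs. Section 1.1 mentions continuing data collection in other procedures and 8.3 mentions clinical testing in others. Neither gives results, and the protocol names no procedures, so use outside gallbladder and liver is permitted but not established.

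**Conclusion.** The point holds in a limited form. As defined, outcomes 3 and 4 cannot be assigned to the LRP, and outcome 1 can be assigned only ambiguously when the failure is at the Magnetic Controller. The conversion definitions in 5.2 and 5.3 conflict and must be reconciled; this part rests on the text alone. Absence of the operation and organ from the 7.4 list means that a breakdown by earlier MSS experience is not secured.

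The size depends on how many failures occur, which the documents do not give. With no failures the issue disappears; with 5 in 100, the LRP-attributable rate is undetermined between 0% and 5% before sampling error is considered. This does not undermine the objective of assessing the combination. It limits what can be said about the new device, and is worth correcting because correction before enrolment is cheap.

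**What to change.** - In 5.2, 7.4 and the CRF, record for each failure of outcomes 1 to 4 and for each conversion a cause: MSS, LRP, both, other (including the endoscope) or undetermined, judged by cause as in 12.4.1.
- Flag events at the Magnetic Controller separately, distinguishing a magnet fault from arm motion or pressure. Do not code them automatically as both, since that would erase the distinction being sought.
- Record the operation and the organ retracted. Tabulate the 5.2 outcomes and device-related adverse events for gallbladder or liver retraction against all other organs.
- Use one definition of conversion in 5.2 and 5.3, with the cause reported alongside it.

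The cost is two or three CRF fields and one extra table. The strata will be small: with no failures, the exact 95% upper limit is 7.1% in a stratum of 50 and 16.8% in one of 20 (illustrative sizes). The table should therefore be read as descriptive, in keeping with 9.1. Cases judged undetermined will leave some of the ambiguity in place.

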5.3 Other Assessments

- Operative time
- Time spent in the Post Anesthesia Care Unit (PACU)
- Length of stay (LOS) (time from admittance to post-anesthesia care unit until hospital discharge)
- Conversion rate (conversion to an open procedure due to inadequate MSS performance)
- Number of required surgeons
- Estimated blood loss
- MSS and Robotic Platform malfunctions
- Patient and Surgeon satisfaction with the system

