6.3 Study Duration

Enrollment of subjects in this study is anticipated to take up to 12 months. Clinical follow-up evaluations will be conducted at discharge, and 7 and 30 days following surgery. The total study duration is expected to be approximately 13 months.

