7.3 Screening/Baseline Evaluation

The Screening visit will occur within 30 days prior to the laparoscopic procedure.

The following evaluations are required at the time of subject screening /baseline:

- Demographic Information: gender, race, age, weight, and height, and smoking status
- Medical / Surgical History
- Pre-operative blood draw for determination of coagulation disorders if warranted
- Urine pregnancy test for women of childbearing potential. Note that if the screening test is more than 1 week prior to the index procedure, a second urine pregnancy test is required within 7 days of the index procedure.

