7.4 Procedure

The Investigator will perform the surgical procedure in accordance with the methods detailed in the Instructions for Use (IFU).

The following intra-operative data will be collected:

- General anesthesia time
- Operative time (from the first incision to the last suture's placement)
- Device and procedure observations
- Number of required surgeons
- Conversion to open surgical procedure

- The need for an additional surgical tool to mobilize the intended organ or tissue
- Estimated blood loss
- Video recording of the overall procedure
- Adverse events

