7.5 Post-Procedure / Hospital Discharge

Before hospital discharge the following data will be collected:

- Length of hospital stay (time from admittance to post-anesthesia care unit until hospital discharge)
- Length of time spent in Post Anesthesia Care Unit (PACU)
- Adverse events, if any

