7.6 Follow-up

All subjects will be asked to return to the investigational site at 7 days and again at 30 days post-procedure according to the study schedule described in **Table 1**. Subjects will be queried about adverse events at these study visits. Study visits should be scheduled as closely as possible to the earlier part of the time period to allow for rescheduling if needed due to last minute schedule changes. Visits not completed within the specified time period will be regarded as deviations.

Table 1: Schedule of Assessments

Assessment	Time Frame			
	Pre-op	Index Procedure & Discharge	7 day follow-up	30 day follow-up
Visit Window	- 30 days	NA	(± 3 days)	(± 7 days)
Informed Consent	√			
Medical History	√			
Demographics	√			
Blood Tests	√			
Pregnancy Test *	√	√		
Intra-operative assessments		√		
Adverse events		√	√	√

* Urine pregnancy test for all women of childbearing potential at pre-op visit and repeated within 7 days of index procedure unless pre-op visit/prior urine pregnancy test was within 7 days of index procedure.

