10 DATA MANAGEMENT

10.1 Data Collection

Data will be collected on paper case report forms (CRF) supplied by the Sponsor. The Site Principal Investigator is responsible for the accuracy and completeness of all study documentation.

Corrections to the CRF must be made by drawing a single line through the incorrect data, entering the correct data beside the incorrect entry, then initialing and dating the correction. Incorrect data must not be obscured. The use of pencil, erasable ink, or correction fluid on CRFs is prohibited. All fields must be completed, e.g. if the item was not done, mark "N/D". If the item is not applicable to an individual case, mark the field "N/A".

CRFs will be printed on 3-part NCR paper (or equivalent) so that both the site and monitor/Sponsor will have copies of the CRFs. One of the three copies may be sent to the Sponsor for remote monitoring. Any other subject

information sent to the Sponsor must be redacted of personal identification information.

A unique study number will be assigned to each subject. All information recorded on the CRF about the subject will be recorded with the study number on it. The main database will contain only the study number to identify the subject. The code with subject name and study number will be maintained in a secured designated location at the site and will be inspected by study monitors and auditors. Any computerized data will be password protected.

Levita Magnetics or its designee will be responsible for database design and management for this study.

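### Does the absence of a satisfaction item from the visit sections leave the section 5.3 satisfaction assessment uncollected?

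*Combined protocol and SAP*

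**What the plan says.** Section 5 opens with a general commitment: "The following endpoints will be evaluated in all subjects who undergo laparoscopic procedures using the Robotic Platform and Magnetic Surgical System". Section 5.3 then lists eight other assessments, the last being "Patient and Surgeon satisfaction with the system". It gives no scale, question or time point.

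The data to be gathered are set out visit by visit:

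- Section 7.3 introduces the baseline list with "The following evaluations are required at the time of subject screening /baseline".
- Section 7.4 gives the intra-operative list, which includes the broad entry "Device and procedure observations".
- Section 7.5 begins "Before hospital discharge the following data will be collected" and names length of stay, recovery-unit time and adverse events.
- Section 7.6 says of days 7 and 30: "Subjects will be queried about adverse events at these study visits".

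Section 6.3 confirms three post-operative contacts: "Clinical follow-up evaluations will be conducted at discharge, and 7 and 30 days following surgery". Section 10.1 states: "Data will be collected on paper case report forms (CRF) supplied by the Sponsor". It also says that no field on those forms may be left blank. In the investigator's statement at the front of the protocol, the investigator undertakes to record what the protocol and the case report forms require. Section 9.1 disclaims any statistical aim and makes descriptive tables optional.

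**The concern.** An assessment promised for all treated subjects should be traceable to a visit, a respondent and a form. Here it cannot be traced within section 7. A coordinator who worked only from the visit lists would have no prompt to ask any patient about satisfaction. A monitor checking the site against section 7 and Table 1 would find nothing to flag. Scheduled contact ends at day 30, so an answer not obtained by then could not be reliably recovered. With up to five sites, questions improvised locally could differ in wording, scale and timing and would be hard to pool. Section 1.1 also mentions patient satisfaction among the hoped-for results of using fewer incisions, which makes the omission look less incidental.

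**Working it through.** No formula or stated figure is involved. The check sets the list in section 5.3 against the collection sections.

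**Listed data items.** Section 7.3 has 4, section 7.4 has 9, section 7.5 has 3 and section 7.6 has 1: 4 + 9 + 3 + 1 = 17. Items naming satisfaction: 0.

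This count makes the gap look larger than it is. Adverse events appear three times (7.4, 7.5 and 7.6), so there are 17 − 2 = 15 distinct items. The 4 baseline items precede any use of the device and could not hold satisfaction with it. That leaves 15 − 4 = 11 distinct items where it might have appeared.

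**Table 1.** The assessment rows are informed consent, medical history, demographics, blood tests, pregnancy test, intra-operative assessments and adverse events: 7 rows, 0 naming satisfaction. Only adverse events is ticked at days 7 and 30. But Table 1 is not a complete inventory. Recovery-unit time and length of stay are plainly collected under section 7.5 and have no row either. Absence from Table 1 therefore does not show that an item goes uncollected.

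**Tracing the eight items of section 5.3.**

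| Item | Where collected |
|---|---|
| Operative time | 7.4 |
| Conversion | 7.4 |
| Number of surgeons | 7.4 |
| Blood loss | 7.4 |
| Recovery-unit time | 7.5 |
| Length of stay | 7.5 |
| Malfunctions | 12.6 |
| Satisfaction | no named point |

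That is 4 + 2 + 1 = 7 traced and 1 not.

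Two of the traced items depend on a generous reading. Malfunctions are found only outside section 7. Conversion in section 5.3 is limited to conversion caused by inadequate performance of the magnetic system, whereas the entry in section 7.4 records conversion without a cause. Read with the same generosity, the surgeon half of satisfaction fits under "Device and procedure observations". The patient half does not, because that entry is intra-operative.

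**How the protocol handles detail elsewhere.** The first two feasibility outcomes in section 5.2 concern whether the platform handles the magnet as the surgeon directs and whether the view is adequate. They have no dedicated line in section 7.4 either and must be recorded through the general observations entry or the forms. Leaving item-level detail to the forms is thus this protocol's usual practice.

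**Effect on results.** Section 5.1 (safety) and section 5.2 (feasibility) make no use of satisfaction. Section 9 states no hypothesis, error rate or precision target, and section 9.2 does not tie the sample size of 100 to any endpoint. No reported result changes with the presence or absence of this item, apart from the item itself.

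**The case for a change.** The best case for a change is that satisfaction alone among the eight items has no named collection point, that the commitment covers all treated subjects, and that the remedy is cheap before enrollment and impossible after day 30. Section 13.4 requires strict adherence to the protocol, and section 13.5 defines deviations as failures to meet its requirements, so a site that never asked would breach no visit requirement. The forms cannot be inspected, so their content cannot be taken for granted.

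Much of this is true. The text of section 7 does not deliver the patient half, and that stands. But it does not follow that satisfaction is not required. Section 5 is itself a requirement, and the investigator's statement binds sites to the forms as well as to the protocol. Sites are not told to work from the visit lists alone. The link to the rationale is also loose: section 1.1 speaks of overall satisfaction after surgery as a general aim of minimally invasive technique, while section 5.3 concerns satisfaction with the system, and the study's own benefits list in section 8.1 does not mention satisfaction. The available remedies (citing the forms, adding a question, or removing the bullet) would leave every safety and feasibility result as it was.

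**Conclusion.** The inconsistency exists, but no change to the plan follows. It is missing operational detail of a kind the sponsor ordinarily supplies when designing the case report forms; no stated rule gives a wrong result. Its size is one of eight items in section 5.3, and strictly only the patient half of that item, in up to 100 subjects. The effect on the safety and feasibility conclusions is none.

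This rests on two assumptions. The first is that the forms carry a satisfaction question or that the sponsor adds one, which the documents neither confirm nor exclude. If it fails, the loss is confined to a descriptive summary of patient satisfaction, and surgeon opinion may still be available from the operative observations. The second is that the study is read as section 9.1 describes it: descriptive and without inferential claims. The conclusion uses only the sections present in the public text and infers nothing from pages that are not.
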